Appendix: Inclusion/Exclusion Criteria Checklist	

#### SCHEMA

# LIST OF ABBREVIATIONS AND DEFINITION OF TERMS

FDG	Fluorodeoxyglucose
IRB	Institutional Review Board
IV	Intravenous
PET/CT	Positron emission tomography – computed
	tomography
PET/MRI	Positron emission tomography – Magnetic
	resonance imaging
ROC	Receiver-Operative-Characteristic
SUV	Standardized Uptake Value

#### 1. OBJECTIVES

#### 1.1 Primary Objective

 To evaluate if PET/CT and PET/MRI scanners provide equivalent results for evaluation of cancer patients

#### 2. BACKGROUND

#### 2.1 Preliminary information

The recent introduction of hybrid PET/MRI scanners in clinical practice (1-3) showed promising initial results for several clinical scenarios (4, 5). More than a decade ago, multimodality imaging was introduced into clinical routine with the development of the PET/CT. Since then, PET/CT has been widely accepted in clinical imaging and has emerged as one of the main cancer imaging modalities. With the recent development of combined PET/MRI systems for clinical use, a promising new hybrid imaging modality is now becoming increasingly available. The combination of functional information delivered by PET with the morphologic and functional imaging of MR imaging (e.g., diffusion-weighted imaging, dynamic contrast-enhanced MR imaging and MR spectroscopy) offers exciting possibilities for clinical applications as well as basic research. However, the differences between CT and MR imaging are fundamental. This also leads to distinct differences between PET/CT and PET/MRI not only regarding image interpretation but also concerning data acquisition, data processing and image reconstruction. PET/MRI is expected to show advantages over PET/CT in clinical applications in which MRI is known to be superior to CT due to its high intrinsic soft tissue contrast. However, as of now, only assumptions can be made about the future clinical role of PET/MRI, as data about the performance of PET/MRI in the clinical setting are still limited (6).

#### 2.2 Study Agent

We will use F FDG and Ga DOTA TATE as the PET radiopharmaceuticals.

#### 2.3 Clinicaltrials.gov

F FDG is an FDA-approved product. Therefore no registration on clinicaltrials.gov is required. Ga DOTA TATE PET/CT is already registered on clinicaltrials.gov.

#### 2.4 Rationale

The Division of Nuclear Medicine and Molecular Imaging at Stanford has two of the most modern PET/CT scanners from GE Healthcare, the Discovery 600 PET/CT and Discover 690 PET/CT scanners. There will be a novel GE PET/MRI scanner installed at the Lucas Imaging Center. This will be the first of this kind to be produced by GE Healthcare. Therefore it is important to determine if PET/CT and PET/MRI scanners provide equivalent results for evaluation of cancer patients.

#### 2.5 Study Design

This is a non-randomized prospective trial. Patients who are referred to Nuclear Medicine for evaluation of extent of cancer and are scheduled to undergo the F FDG or Ga DOTA TATE PET/CT will be asked to have the scan repeated on the same day using PET/MRI scanner. There will be a single injection of F FDG or Ga DOTA TATE followed by the PET/CT scan and immediately after by the PET/MRI scan. There will be no additional radiation to the patient. This is because only one injection of F FDG or Ga DOTA TATE will be given and the MRI uses non-ionizing radiation.

# 3. PARTICIPANT SELECTION AND ENROLLMENT PROCEDURES

#### 3.1 Inclusion Criteria

- Patient is  $\geq$  18 years old at the time of the scan
- Patient provides written informed consent
- Patient is diagnosed with cancer
- Patient is capable of complying with study procedures
- Patient is able to remain still for duration of imaging procedure (approximately 90 minutes total for PET/CT and PET/MRI)

#### 3.2 Exclusion Criteria

- Patient is < 18 years old at the time of the drug administration
- Patient is pregnant or nursing
- Metallic implants (contraindicated for MRI)
- Renal function impairment preventing administration of MRI contrast

#### 3.3 Informed Consent Process

All participants will be provided a consent form describing the study with sufficient information for participants to make an informed decision regarding their participation. Participants must sign the IRB approved informed consent prior to participation in any study specific procedure. The participant must receive a copy of the signed and dated consent document. The original signed copy of the consent document must be retained in the medical record or research file.

#### 3.4 Study Timeline

#### 3.4.1 Primary Completion:

The study will reach primary completion 24 months from the time the study opens to accrual.

#### 3.4.2. Study Completion:

The study will reach study completion 48 months from the time the study opens to accrual.

#### 4. IMAGING AGENT INFORMATION

#### 4.1 Study Agent

We will use F FDG or Ga DOTA TATE as the PET radiopharmaceuticals. These will be used as standard of care. The administered dosage is 10-12 mCi iv for F FDG and 5-7 mCi for Ga DOTA TATE.

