#### 10. MEASUREMENTS

#### **10.1 Primary outcome measure**

We will evaluate the maximum standardized uptake value (SUVmax) of F FDG or Ga DOTA TATE in the lesions detected with both scanners. There are now several papers based on other vendors' scanners (no GE PET/MRI scanner built yet). The authors showed that in oncologic patients examined with PET/CT and PET/MRI, the SUVmax values generally correlate well in normal organ tissues. SUVmax derived from PET/MRI can be used reliably in clinical routine. Differences observed between MRI and CT derived SUV values may be attributed to the time-delay between the PET/CT and PET/MRI scans or biologic clearance of radiotracer (*10, 11*).

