#### 11.5. **Primary Analysis**

#### 11.1.1. Analysis Population

Analysis population: all lesions identified by either modality (per-lesion analysis).

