#### 11.1.2. Analysis Plan

Normal quantile plots of  $SUV_{max}$  for each scanner will be prepared to assess to what extent the distribution can be approximated by the normal distribution, and to suggest a suitable transformation if not. The distribution of  $SUV_{max}$  for each scanner will be summarized with means, standard deviations, range, median and upper and lower quartiles. The distribution of the difference ( $SUV_{max}$ \_PET/CT –  $SUV_{max}$ \_PET/MRI) (difference of transformed values if applicable) will likewise be summarized. Cumulative distribution (waterfall plots) may be prepared to assist in the evaluation of the results. Patient clinical and demographic characteristics will be summarized using relevant summaries (proportions for categorical variables, means and standard deviations for continuous variables.

The mean difference plus or minus twice the standard deviation of the difference will be calculated as a measure of absolute accuracy. The relative accuracy will be calculated by dividing the preceding interval by the arithmetic average of the mean  $SUV_{max}$  of the two scanners. The interpretation of these intervals is that we can expect that approximately 95% of future differences to lie in these intervals. A paired t-test will be used to aid in the interpretation of the results. Sensitivity analyses may be conducted using linear mixed effects models to account for possible clustering of lesions within patients.

The difference of  $SUV_{max}$  measures will be correlated with patient and lesion characteristics and with time after injection using the appropriate method (Pearson correlation for continuous variables such as age and time from injection, two-sample t-tests for binary attributes (sex) and analysis of variance for categorical variables).

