#### 11.7. Accrual estimates

We expect the accrual of 100 patients. There are approximately 4500 patients scanned each year using PET/CT for cancer, of which approximately 100 patients are Ga68 DOTA TATE PET/CT patients. We plan to enroll 15 participants/year and this is easily achievable given our experience with other protocols.

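### The primary analysis pools FDG and DOTATATE lesions into one mean difference and one set of limits, so the 95% claim need not hold for each tracer

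*Combined protocol and SAP*

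**What the plan says.** Section 4.1 states: "We will use 18 F FDG or 68 Ga DOTA TATE as the PET radiopharmaceuticals". Each patient is injected once, with either FDG or DOTATATE (2.5, 4.1, 5.2). Section 10.1 defines one endpoint for both tracers, SUVmax "in the lesions detected with both scanners". Section 11.1.1 has no tracer stratum: "Analysis population: all lesions identified by either modality (per-lesion analysis".

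Section 11.1.2 then sets out a single summary: "The mean difference plus or minus twice the standard deviation of the difference will be calculated as a measure of absolute accuracy". A relative version divides that interval by the average of the two scanners' means. The stated reading is that "we can expect that approximately 95% of future differences to lie in these intervals". On testing: "A paired t-test will be used to aid in the interpretation of the results". Clustering is optional and concerns patients only: "Sensitivity analyses may be conducted using linear mixed effects models to account for possible clustering of lesions within patients".

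Three other places bear on the point.
- 11.1.2 allows a transformation if the normal quantile plots suggest one, and relates the difference to features of the patient and the lesion. It names age, time from injection and sex; tracer is not named.
- 11.6 uses one CV and one pair of correlations for both tracers.
- 11.7 gives about 4500 PET/CT cancer patients a year, "of which approximately 100 patients are Ga68 DOTA TATE PET/CT patients". It sets no number per tracer among the 100 patients planned.

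**The concern.** A future patient is scanned with one tracer, so a statement about where future differences will fall is useful only if it holds for that tracer. Section 10.1 itself offers clearance of the radiotracer, and the delay between scans, as explanations for differences between scanners. Clearance can depend on the tracer, so the plan names a possible tracer-dependent source of bias and then averages over tracers.

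If the biases or SDs differ, the pooled limits are weighted towards the tracer with more lesions and can be off-centre or too narrow for the other. If the biases have opposite signs, they partly offset each other in the mean and the t-test. The report could then claim agreement for both tracers on the strength of one.

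**Working it through.** **The plan's own figures.** Inputs from 11.6: CV 0.38 for both scanners, correlation r = 0.5 or 0.9, 80% power. No alpha is stated; two-sided 0.05 is assumed. Taking the CV as the log-scale SD:

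- SD of the difference = 0.38 × √(2(1 − r)) = 0.380 at r = 0.5 and 0.170 at r = 0.9.
- Detectable relative difference = exp[(1.960 + 0.842) × SD/√N] − 1.
- N = 200: 7.8% (r = 0.5) and 3.4% (r = 0.9); stated 8% and 3.4%.
- N = 100: 11.2% and 4.9%; stated 11% and 5%. The 5% is printed beside 200 patients but fits 100.

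The figures reproduce. They do not address tracer, and the SDs carry over to the next step.

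**Effect of pooling when biases differ.** Let p be the DOTATATE share of lesions, mF and mD the tracer biases, and s the within-tracer SD.

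- Pooled mean m = (1 − p)mF + p·mD
- Pooled SD S = √(s² + p(1 − p)(mF − mD)²)
- Limits m ± 2S; coverage for a tracer with bias μ = Φ((m + 2S − μ)/s) − Φ((m − 2S − μ)/s)

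Assumed biases: mF = +0.10, mD = −0.10. These are not from the documents.

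Worked case, p = 0.10, r = 0.9: m = 0.90 × 0.10 − 0.10 × 0.10 = 0.080. S = √(0.170² + 0.09 × 0.04) = 0.180. Limits −0.280 to 0.440. For DOTATATE the standardised limits are −1.06 and 3.18, so coverage is 85.5%. For FDG they are −2.24 and 2.00, so coverage is 96.5%.

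| r | p | Pooled mean | Pooled SD | FDG coverage | DOTATATE coverage |
|---|---|---|---|---|---|
| 0.9 | 2.2% | 0.096 | 0.172 | 95.8% | 80.9% |
| 0.9 | 10% | 0.080 | 0.180 | 96.5% | 85.5% |
| 0.9 | 25% | 0.050 | 0.191 | 96.9% | 91.3% |
| 0.9 | 50% | 0.000 | 0.197 | 95.7% | 95.7% |
| 0.5 | 2.2% | 0.096 | 0.381 | 95.5% | 92.6% |
| 0.5 | 10% | 0.080 | 0.385 | 95.7% | 93.3% |

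At 50/50 the mean is exactly zero, and the t-test rejects no more often than its 5% level although both tracers are biased. Coverage holds there only because the SD has grown from 0.170 to 0.197.

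**Unequal spread, equal bias.** Assume DOTATATE's SD is twice FDG's, p = 10%, r = 0.9. S = 0.170 × √(0.9 + 0.1 × 4) = 0.194. Coverage is 97.7% for FDG (±2.28 SD) and 74.6% for DOTATATE (±1.14 SD).

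**No transformation.** Assume DOTATATE SUVmax is k times FDG SUVmax, with p = 20% and no scanner bias. Pooled SD over FDG SD = √(0.8 + 0.2k²) = 1.26 at k = 2 and 2.00 at k = 4. By simulation with lognormal values, CV 0.38 and r = 0.9, coverage is about 98% (k = 2) to 99.8% (k = 4) for FDG. For DOTATATE it is about 82 to 83% (k = 2) and 73 to 74% (k = 4). On the log scale the factor k drops out of the difference and both tracers have 95.4%.

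**Tracer mix.** 100/4500 = 2.2%. If enrolment followed the clinic, 100 patients would include about 2 on DOTATATE, with a binomial probability of 0.106 + 0.240 + 0.270 = 0.62 of two or fewer. But 11.7 plans 15 participants a year against about 100 DOTATATE patients a year, so a far larger share is equally feasible. The weights in the analysis are lesion counts, which are not given either.

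**The case against.** The strongest reply is that nothing in the documents shows the tracers to differ. No tracer-specific bias, sign or SD is given, and 10.1 indicates no direction. If the tracers agree, pooled limits serve both. This stands: the coverage figures are conditional.

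Second, the transformation step in 11.1.2 removes a pure difference in scale, so the untransformed figures apply only if no transformation is made. This also stands. The step does not remove differences in bias or in log-scale SD.

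Third, the exploratory analysis could take tracer as a categorical variable. With biases of ±0.10, r = 0.9 and 100 independent pairs, such a comparison has over 99.9% power at 50/50 and 99.7% at a 20% DOTATATE share; at r = 0.5 and 50/50 it has about 74%. So full cancellation would often be noticed if someone ran the test. With 2 and 98 patients it would usually be missed: at r = 0.9 the standard error is 0.170 × √(1/2 + 1/98) = 0.121, 0.20/0.121 = 1.65, and power is about 38%. In any case tracer is not named, and the test compares means. It gives no tracer-specific limits and leaves the pooled interval as it is.

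A reader might infer that the pooled limits describe neither tracer. The documents do not support that. At the clinic's 2.2% mix the limits nearly are the FDG limits, and only DOTATATE would be misdescribed.

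**Conclusion.** The plan pools two tracers into one set of limits and attaches a coverage claim that need not hold for each. That much follows from the text. The size does not: it rests on assumed tracer differences and an unknown mix. Under log-scale biases of ±0.10 and r = 0.9, DOTATATE coverage falls to about 81 to 86% at shares of 2.2 to 10%, with FDG at about 96%. At r = 0.5 DOTATATE stays at about 93%. Without a transformation, a 2- to 4-fold higher DOTATATE SUVmax at a 20% share gives about 73 to 83%.

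Two stronger readings go too far. One is that the 95% statement is false for each tracer; it fails only if the tracers differ, which the documents leave open. The other is that opposite effects will hide each other; full cancellation in this example needs a mix near 50/50, and it widens the SD, so the limits do not conceal it entirely. The 2.2% is clinic volume, not an enrolment rule, and should not be taken as a forecast of DOTATATE numbers. The sample-size figures are not wrong on this account.

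This is an inexpensive improvement worth making before analysis, not a flaw that invalidates the study.

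**What to change.** In 11.1.2:

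- Report the mean difference and limits of agreement separately for FDG and DOTATATE as the primary display, and keep the pooled result as secondary.
- Name tracer as a prespecified fixed effect in the mixed model of scanner differences, with a patient random effect. Allow tracer-specific variance only where numbers permit; two or so patients would not support it.
- Report patients and lesions per tracer. Label a tracer with few patients as descriptive and limit the conclusion accordingly. Stating a planned number per tracer in 11.7 would settle this in advance.

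The change is SAP wording. Tracer should be available from the radiology order (4.3), though no case report form is shown to confirm it. The price is precision in the smaller group. By the formula above, with one pair per patient, a 90/10 split gives detectable differences of 11.9% and 40% at r = 0.5, or 5.1% and 16% at r = 0.9, against 11.2% and 4.9% for the pooled 100. A 50/50 split gives 16.2% and 7.0% per tracer.

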#### 4.2 Specify the source of the study agent.

Molecular Imaging Program at Stanford Lucas Cyclotron Radiochemistry Facility [name]

# 4.3 Describe how the agent will be requested and provide mailing address and phone number.

Ordered in Radiology Information System (RIS), address per above.

#### 4.4 Agent Accountability

RIS is password protected and part of the electronic medical records.

#### 5. IMAGING SPECIFICS

#### 5.1 Modality or Modalities to be used

PET/CT & PET/MR

#### 5.2 Details of Imaging (i.e. dynamic, static, number of scans, etc.)

Whole-body (skull base to mid-thighs) PET/CT images will be obtained using the GE PET/CT 600 and 690 scanners (GE Healthcare) per standard oncologic protocols (7). In brief, PET/CT images will be acquired in 3D mode at 45-60 minutes after injection of 10-12 mCi of F FDG or 5-7 mCi of Ga DOTA TATE. The PET emission scan is corrected using segmented attenuation data of the CT scan. The PET images are reconstructed with a standard iterative algorithm (OSEM, two iterative steps, 28 subsets) using GE software release 5.0. All images are reformatted into axial, coronal, and sagittal views and viewed with the software provided by the manufacturer (AW, GE Medical Systems).

Immediately after completion of the PET/CT exam, the patients will be transferred to the PET/MRI suite at the Lucas Imaging Center and undergo the PET/MRI image acquisition with the least delay. Acquisition will start in the pelvic region and move toward the head. First, a localizer MRI scan will be performed to define the table positions. After correct positioning of the spatial acquisition windows will be ensured, the combined PET/MRI acquisition will be initiated with 3-5 table positions at a 4-min acquisition time per table position. First, a coronal 2-point Dixon 3-dimensional volumetric interpolated breath-hold T1weighted MRI sequence will be acquired at each table position and used for the generation of attenuation maps and for anatomic allocation of the PET results. Simultaneously with the start of the Dixon MRI sequence, the PET acquisition will start at the same table position, thus ensuring optimal temporal and regional correspondence between MRI and PET data. The PET acquisition time will be 4 min per table position, taking delayed acquisition times and radioactive decay into account. After completion of the PET acquisition, the table will be moved to the next table position and the procedure will be repeated. In the thorax and abdomen regions, the MRI scans will be acquired during breath-hold in shallow inspiration, similarly to the acquisition of the low-dose CT (8). Other sequences may also be used as needed (9). Multiplanar pre- and post-contrast MR images may be obtained at multiple stations as needed. Images will be reformatted into axial, coronal, and sagittal views and viewed with the software provided by the manufacturer (AW, GE Medical Systems).

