#### 5.3 Details of processing/analysis

The PET/CT scans will be interpreted by ABNM certified Nuclear Medicine physicians, while the PET/MRI scans will be reviewed by ABNM certified Nuclear Medicine physicians and ABR certified Radiologists. All these investigators have significant clinical experience and will be blinded to the participants' medical history and the results of other imaging modalities. Consensus read will be obtained for each scan. Each lesion will be tabulated and a comparison of lesion detection by each scanner will be conducted.

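### The plan does not require PET/MRI to cover the stated PET/CT range, so the lesion detection comparison can count lesions one scanner never imaged as missed by it.

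*Combined protocol and SAP*

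**What the plan says.** Section 5.2 sets the PET/CT range: "Whole-body (skull base to mid-thighs) PET/CT images will be obtained".

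For PET/MRI, the same section gives three things:

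- a start and a direction: "Acquisition will start in the pelvic region and move toward the head";
- an extent: "the combined PET/MRI acquisition will be initiated with 3-5 table positions at a 4-min acquisition time per table position";
- a planning step: "First, a localizer MRI scan will be performed to define the table positions".

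It gives no lower or upper anatomical limit for PET/MRI, no length per table position, and no statement that the positions must reproduce the PET/CT range. Section 2.5 describes the second examination only in general terms: patients "will be asked to have the scan repeated on the same day using PET/MRI scanner".

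Two passages then define which lesions are compared. Section 5.3 says "Each lesion will be tabulated and a comparison of lesion detection by each scanner will be conducted". Section 11.1.1 defines the primary analysis population as "all lesions identified by either modality (per-lesion analysis". Neither mentions the field of view. Section 10.1, by contrast, frames the primary SUVmax outcome on lesions seen by the two scanners together, and section 11.1.2 analyses within-lesion SUVmax differences.

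**The concern.** The only objective, in section 1.1, is whether the two scanners give equivalent results. A paired comparison of detection answers that question only if each scanner had the chance to show each lesion. Where one scanner did not acquire a lesion's location, its failure to show the lesion says nothing about its performance. The plan has no step that separates this case from a true miss. The readers in section 5.3 are blinded to the other modality, so the reading itself will not reveal it. The plan also does not ask for the limits of each scan to be recorded, so its data will not necessarily allow the two cases to be told apart later.

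This is a different problem from a lesion that lies in both fields and is seen on only one scanner. That lesion is real evidence about detection and belongs in the comparison.

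**Working it through.** The plan states no figure on this point, so there is none to reproduce. The check has three steps.

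**1. Coverage.** Section 5.2 gives the number of table positions, b = 3 to 5, but not the axial field per position (F) or the overlap (v). As assumptions from outside the documents, take F = 15 to 26 cm and v = 0 to 35%. The length covered is

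L = F × [1 + (b - 1)(1 - v)].

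| b | Shortest (F = 15, v = 35%) | Middle (F = 25, v = 25%) | Longest (F = 26, v = 0) |
|---|---|---|---|
| 3 | 15 × 2.30 = 34.5 cm | 25 × 2.50 = 62.5 cm | 26 × 3 = 78 cm |
| 4 | 15 × 2.95 = 44.25 cm | 25 × 3.25 = 81.25 cm | 26 × 4 = 104 cm |
| 5 | 15 × 3.60 = 54 cm | 25 × 4.00 = 100 cm | 26 × 5 = 130 cm |

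The permitted extents run from 34.5 to 130 cm. An examination within section 5.2 could leave part of the PET/CT range unscanned or could cover it fully. The documents do not settle which.

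**2. Detection comparison (sections 5.3 and 11.1.1).** Let f be the share of PET/CT lesions that lie outside the PET/MRI field, and d the share of the remaining PET/CT lesions that PET/MRI shows. If every tabulated lesion counts, apparent PET/MRI detection is (1 - f) × d, which cannot exceed 1 - f.

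| f (illustrative) | d = 100% | d = 90% |
|---|---|---|
| 2% | 98% | 88.2% |
| 5% | 95% | 85.5% |
| 10% | 90% | 81% |
| 20% | 80% | 72% |

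The documents give neither f nor d. The same identity works the other way: if a share g of PET/MRI lesions lies outside the PET/CT range, apparent PET/CT detection cannot exceed 1 - g.

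**3. SUVmax analysis (sections 10.1 and 11.1.2).** The mean difference, the interval of plus or minus two standard deviations, and the paired t-test each need a value from both scanners. A lesion outside one field has only one value. Section 11.1.2 gives no rule for imputing the other, so the lesion contributes no difference and drops out. This assumes that the scanner means in the divisor of the relative interval are taken over the same pairs.

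**The case against.** The strongest reply is that matched coverage was intended. Section 2.5 calls the PET/MRI a repeat of the scan. Section 5.2 uses a localizer to set the table positions and has their placement confirmed before acquisition, so three to five may simply reflect patient length. Starting at the pelvis gives the order of acquisition, not a lower boundary, because the first position has its own unstated length. This stands. A reader might infer that the two scans as written image different anatomy, for example that a proximal femur lesion must lie below the PET/MRI field. The documents do not support that: they permit a mismatch but do not state one.

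It can also be said that detection is a minor part of the plan. It appears in one sentence of section 5.3, has no outcome measure in section 10 and no statistic in section 11, and no text says that an out-of-field lesion is a miss. That is correct, and it limits the weight of the point. But detection by scanner is a planned comparison under the sole objective, and nothing in the text excludes such lesions from it.

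A reader might further infer that the primary SUVmax result is biased. It is not biased by this route, as step 3 of the working shows.

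**Conclusion.** The point holds for the lesion detection comparison only. The plan fixes the PET/CT range, leaves PET/MRI coverage untied to it, and compares detection over all lesions seen on either scanner with no common-field rule. Taken literally, this mixes coverage with scanner performance.

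The size cannot be determined from the documents. The ceiling of 1 - f is exact, but every value of f shown is illustrative.

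The direction cannot be determined either. It is tempting to conclude that the bias runs against PET/MRI because its extent is the variable one, but PET/MRI could also extend above the skull base, beyond the PET/CT range. It is equally tempting to say that three positions reach only 3/5 = 60% of the needed length. That assumes a patient who needs five positions receives three, which nothing in the plan says will happen.

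The change is worth making because it removes an artefact from the equivalence question at little cost. It does not affect the sample size calculation in section 11.6.

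**What to change.** - **Sections 5.3 and 11.1.1:** restrict the detection comparison to lesions inside the field of view acquired by both scanners in that patient. Tabulate lesions outside the common field separately, by scanner, and count them as missed by neither.
- **Data collection:** record the upper and lower limits of each PET/CT and PET/MRI acquisition, so that the common field can be established for each patient.
- **Section 5.2:** reconcile the PET/MRI coverage with the stated PET/CT range.
- **Sections 10.1 and 11.1.1:** reconcile the lesion set for the SUVmax analysis, which one describes as lesions seen by both scanners and the other as lesions seen by either.

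The cost is wording in these sections, two recorded limits per scan, and the loss of a few lesions from the detection comparison; they are still reported in the separate table. If the two ranges are aligned, the documents do not show whether five positions always suffice: under the assumptions in the working, five positions reach between 54 and 130 cm. The common-field rule protects the comparison even where alignment is not achieved in a particular patient.
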